4.1.5 Controlling for Contamination

Access to interventions will be restricted to those assigned to each intervention arm, via the provision of unique access links (Arm 1: Dialogue-Based Webinar) and unique user logins (Arm 2: Social Media Website). To audit for inadvertent contamination across arms, we will monitor who registers for and accesses each intervention on a weekly basis, removing those without legitimate access. During data cleaning we will review participants who may have been exposed to content from more than one trial arm, and make decisions about the removal of these data to control for the influence of contamination.

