4.4.5 Comparator

LTCWs will be directed to COVID-19 vaccine information on the CDC website (<https://www.cdc.gov/coronavirus/2019-ncov/vaccines/index.html>). The CDC website addresses common questions about the COVID-19 vaccines and provides information on related topics, such as specifics about getting vaccinated and staying up to date on the vaccines and boosters. To address concerns of intervention inferiority, LTCWs will be given access to active trial arms shown to have impact, after their 6 month follow-up.

An enhanced usual practice refresher will also be delivered to all participants assigned to this arm one week prior to their T2 survey invitation (see Figure 2). The refresher will be an email with a link to COVID-19 vaccine information on the CDC website.

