As-treated analysis of primary and secondary outcomes. Primary and secondary outcomes will also be assessed amongst participants who were exposed to their relevant primary study intervention.

Contextual factors. We will identify contextual factors that may contribute to COVID-19 vaccine intentions and decisions, including personal COVID-19 and vaccine experiences and participation in other COVID-19 vaccine research, using a single self-developed question.

External contextual factors. Outside of the study surveys and throughout the trial, we will monitor external factors that may impact participants' views and actions towards the COVID-19 vaccines. This may include monitoring policy and mandate changes for LTCWs and changes in the nature of the pandemic, among other things.

Participant characteristics. We will assess several participant characteristics including age, gender (adapted from^{56,57}), zip code, educational attainment (adapted from⁵⁸), race and ethnicity (adapted from⁵⁸), health insurance (adapted from^{58,59}), health literacy^{60,61}, religiosity⁶², LTCW role, duration of experience in long-term care, extent influenced by others regarding COVID-19 vaccination, and baseline vaccination status.

Intervention engagement. We will monitor the extent to which participants engage with their assigned primary and refresher intervention content. We will collect online activity data (i.e., social media website user history, webinar attendance records, email click rates) and participant self-reported engagement data via surveys. We will prioritize the use of online activity data to minimize potential measurement error³⁶. However, survey questions may be used where online activity data is not available or is incomplete; for example, to determine engagement with the webinar refresher recording (adapted from³⁶) and enhanced usual practice information. Data on engagement will be used to inform secondary trial analyses, as well as Aim 3.

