4.7.4 Blinding

Due to the nature of the interventions and intervention delivery, it is not possible to blind facilitators, research team members or participants to the allocation. Participants may be aware that they are in a control or intervention arm. The data analyst will be blinded to arm allocation where possible.

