P-values ≥ 0.0001 will be reported to 4 decimal places; p-values less than 0.0001 will be reported as " <0.0001 ". The mean, standard deviation, and any other statistics other than quantiles, will be reported to one decimal place greater than the original data. Quantiles, such as median, minimum, or maximum will use the same number of decimal places as the original data. Estimated parameters, not on the same scale as raw observations (e.g. regression coefficients) will be reported to 3 significant figures.

Adherence to interventions

Analysis of both intention-to-treat (ITT) and as-treated populations will be performed. All participants who are randomized to a trial arm will be included in the ITT analyses. Participants who adhere to major engagement criteria for their primary intervention will be included in the as-treated analyses.

Analysis methodology

Aim 1

To compare the impact of two interventions delivered online: 1) a dialogue-based webinar (webinar) using the existing COVID-19 Option Grid conversation aid and, 2) an interactive and, dynamic, and multi-component social media web application (social media website), compared to enhanced usual practice (link to Centers for Disease Control (CDC) vaccine website), on COVID-19 vaccine confidence (primary outcome), and other secondary outcomes among LTCWs. We hypothesize that each intervention will be superior to enhanced usual practice at increasing vaccine confidence (*Hypothesis 1.1*) and that the dialogue-based webinar intervention will be superior to the social media arm at increasing vaccine confidence (*Hypothesis 1.2*).

Corresponding analyses

Primary outcome

The primary outcome is the binary classifier of vaccine confidence derived from the three-item Vaccine Confidence Index (VCI), evaluated at 3 weeks post-randomization, which will be analyzed by randomization arm. The determined binary predictors of intervention outcomes will be compared using two-proportion z-tests to identify significant differences between each intervention and enhanced usual practice (Arm 1 vs Arm 3 & Arm 2 vs Arm 3 - superiority analyses) and between the intervention arms (Arm 1 vs Arm 2 - two-tailed equivalency analysis).

Secondary outcomes

- *Change from baseline in COVID-19 Vaccine Confidence.* Analysis of change from

baseline will be based on a binary classifier whether the average score increases (1) or does not increase (2) at T1, T2, and T3 versus baseline.

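### The protocol allows data to be removed for cross-arm exposure without a rule or a named analysis set, which would conflict with the ITT definition if applied to the primary analysis

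*Combined protocol and SAP*

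**What the plan says.** Section 4.1.5 describes three steps against contamination.

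- **Restriction.** "Access to interventions will be restricted to those assigned to each intervention arm", through unique links for the webinar and unique logins for the social media website.
- **Audit.** "we will monitor who registers for and accesses each intervention on a weekly basis, removing those without legitimate access".
- **Data cleaning.** "we will review participants who may have been exposed to content from more than one trial arm", and the team will then "make decisions about the removal of these data to control for the influence of contamination".

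On who is analysed, Appendix B (Adherence to interventions) says: "All participants who are randomized to a trial arm will be included in the ITT analyses". Section 4.8.2 defines ITT by the arm assigned and plans an as-treated analysis beside it.

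Appendix B has no contamination rule. The exclusions it does state are for lack of valid primary outcome data at T0 and T1 (Duplicate and missing data) and for fraudulent enrolment (Fraudulent enrollment). Under Methods to minimize bias it also plans a naïve analysis of the unmodified data by ITT assignment, as an initial estimator, and independent replication of the primary analyses by the DSMB statistician.

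**The concern.** Exposure to another arm's content happens after randomisation and may be related to how actively a person seeks information, and so to vaccine confidence. Removing people on that basis can break the comparability that randomisation provides. Section 4.1.5 leaves the following open:

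- **What counts as exposure.** Both interventions share the same major topics and the same resident video (section 4.4.2), and no access restriction is described for the comparator: "LTCWs will be directed to COVID-19 vaccine information on the CDC website". Without a definition, the trigger could be read narrowly or very broadly.
- **Who decides, and what they know.** Judging cross-arm exposure means comparing access with assignment, so the review cannot be blind to arm. Section 4.7.4 says that "it is not possible to blind facilitators, research team members or participants to the allocation". Nothing bars those deciding from seeing outcomes, which will have been collected by the time data are cleaned.
- **Which analysis is affected.** Nothing limits removal to the as-treated set.

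At stake is the primary comparison of T1 confidence rates. A discretionary exclusion could shift it and alter the type I error that the Bonferroni rule is meant to control.

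**Working it through.** **1. The two rules side by side.** Section 4.1.5 permits removal after randomisation on the basis of exposure. Appendix B puts every randomised participant in the ITT analyses, and section 4.8.2 analyses by assigned arm. Both can hold only if removal is kept out of the ITT analyses. Neither document says that it is.

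**2. The plan's own power figure.** Section 4.6 states 600 per arm, 80% power, an 8-point difference and two-sided alpha 0.05. The control rate is not given. Assuming 0.46 vs 0.54 (near maximum variance) and a pooled z-test:

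- SE under the null = √(2 × 0.50 × 0.50 / 600) = 0.02887
- SE under the alternative = √(2 × 0.2484 / 600) = 0.02878
- Power = Φ[(0.08 − 1.96 × 0.02887) / 0.02878] = Φ(0.81) = 79.2%

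At 0.30 vs 0.38, power is 83.4%. The stated 80% is reproduced. Keeping everyone in the ITT set leaves 600 per arm, so the fix does not change this figure.

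**3. Size of a possible shift.** The documents give no removal rate, no split by arm and no outcome gap, so all three are assumed here. Let a fraction r be removed from one arm only.

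- With g the gap between removed and kept, shift = r × g. For g = 20 points: r = 0 gives 0, r = 0.05 gives 1.0 point, r = 0.10 gives 2.0 points.
- With d the gap between removed and the whole-arm average, shift = d × r / (1 − r). For d = 20 points: r = 0.05 gives 1.05 points, r = 0.10 gives 2.22 points.

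Removing less confident people raises that arm's rate; removing more confident people lowers it. If g = 0, the shift is zero at any r.

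**4. Effect on the superiority test.** The inputs are no true effect, 600 per arm, an assumed control rate of 0.46, removal from one intervention arm only, and the Appendix B cut-off of 2.15 standard errors (one-sided error about 0.016). The gap is d = 20 points from the arm average.

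| Removed | Their confidence | Shift (points) | One-sided error |
|---|---|---|---|
| 0% | – | 0 | about 0.016 |
| 5% | 20 points below average | +1.05 | 0.037 |
| 10% | 20 points below average | +2.22 | 0.081 |
| 5% | 20 points above average | −1.05 | 0.006 |
| 10% | 20 points above average | −2.22 | 0.002 |

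For the 10% row with less confident people removed: the kept rate is (0.46 − 0.10 × 0.26) / 0.90 = 0.4822 with n = 540, and the SE is about 0.0296. The error is then 1 − Φ(2.15 − 0.0222 / 0.0296) = 1 − Φ(1.40) = 0.081. At 360 per arm, the number left after the 40% attrition considered in section 4.6, the two errors for less confident people become 0.031 and 0.058.

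**The case against.** **Removal may never touch ITT.** Section 4.1.5 names no analysis set. Section 4.8.2 refers the detailed methods to Appendix B, which says that primary and secondary analyses follow the SAP and lists no contamination exclusion. On that reading cross-exposed participants stay in ITT. This stands as a fair reading, and it is why the conflict is conditional. It does not settle the matter, because no text limits the removal in section 4.1.5. Appendix B's statement that all randomised participants are included is also already qualified by its own T0/T1 data requirement and fraud exclusion, so it cannot be relied on to override a removal provision elsewhere.

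**Safeguards exist.** A reader might infer that any bias would be uncheckable. That goes too far: comparing the naïve analysis with the main one would help show what removals did. But the naïve result is only an initial estimator, and replication by the DSMB statistician is not described as a review of who was removed.

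**Removal need not fall on the intervention arms.** Because the CDC site is open to anyone, a reader might infer that nearly all removals would come from Arms 1 and 2. The documents do not support this. The audit described tracks access to the gated interventions, so it would catch Arm 3 participants who get in as well as crossovers between Arms 1 and 2. Engagement monitoring covers assigned content ("We will monitor the extent to which participants engage with their assigned primary and refresher intervention content"), and no measurement of CDC visits in Arms 1 and 2 is described.

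**Blinding.** The decision-maker is not named, and section 4.7.4 blinds the analyst to arm where possible. It is therefore not documented that people who know the outcomes would decide; the plan simply does not prevent it.

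**The number affected may be near zero.** Individual links, logins and weekly audits limit crossover. This stands, and the illustrated range therefore starts at zero.

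**Conclusion.** The point holds as an unreconciled conflict. Section 4.1.5 gives an open-ended power to remove data after randomisation, and Appendix B and section 4.8.2 leave no room for it in an ITT analysis. It goes beyond missing detail, because a removal provision is stated and nothing keeps it away from the primary result.

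Its size cannot be fixed from the documents. With 0 to 10% removed from one arm and a 20-point gap, both assumed, the shift is 0 to about 2 points in either direction against the 8-point design effect. It is zero if removal is unrelated to confidence. Neither the arm balance nor the direction is established. The plan should be changed because the bias is avoidable at almost no cost, not because a particular bias has been shown.

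**What to change.** - In section 4.1.5, delete the removal provision as it applies to ITT analyses. State there and in Appendix B that cross-exposed participants stay in their randomised arm in all ITT analyses.
- Report the number cross-exposed by arm.
- Allow exclusion only in a sensitivity or as-treated analysis. Fix the exposure definition before outcomes are examined by arm, name who applies it, and keep that person blind to outcome.
- Base the definition on logged access to the gated interventions, and not on viewing the public CDC site.

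The cost is a short amendment to the protocol and Appendix B. Sample size and stated power do not change. The downside is that true contamination will slightly dilute the estimated effect, as an ITT analysis intends.

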4.2 Setting

The randomized trial will be conducted entirely online, and will be open to LTCWs residing anywhere in the United States. We will use a combination of online and in-person recruitment strategies. In-person recruitment will occur at a convenience sample of LTC settings in North Carolina, identified by our collaborator ([name]), who has extensive professional LTC experience and trusted relationships with LTC leaders in the North Carolina area. Settings will include large and smaller size for-profit and not-for-profit nursing homes and continuing care retirement communities in both rural and urban locations. Additional settings will include the New England region.

4.3 Participants

4.3.1 Randomized Controlled Trial (Aims 1 and 2)

Eligible participants will include vaccinated and unvaccinated LTCWs who self-identify as: 1) being 18 years and older, 2) living in the United States, 3) having worked in a long-term care setting in the past two years, 4) able to verify their LTCW status, 5) not currently pregnant or breastfeeding, and 6) able to read, write, and understand English, and 7) being at least somewhat worried about the COVID-19 vaccines and/or not having received any COVID-19 booster vaccine (see Table 2).

Eligible LTC settings will include nursing homes, skilled nursing facilities, assisted living facilities, home health care, hospice care, and retirement communities. The two-year timeframe will avoid excluding those who are currently unemployed, and will approximately cover the duration of time since the COVID-19 pandemic began. To ensure a high proportion of study participants represent our low confidence target group, we will use two criteria – worry about the vaccines and booster uptake – to screen participants for eligibility. These criteria are based on a preliminary analysis of panel survey data, which found associations between booster intent, worry about the vaccines, and vaccine confidence.

Table 2. Screening questions and eligibility criteria

Question	Eligible Response(s)	Ineligible Response(s)
Can you read, write, and understand English? (adapted from ³⁶)	Yes	No
How old are you?	18-19 years; 20-24 years; 25-29 years; 30-34 years; 35-39 years; 40-44 years; 45-49 years; 50-54 years; 55-59 years; 60-64 years; 65 years or older	Less than 18
Do you live in the United States?	Yes	No
This study is for long-term care workers. We must be sure that everyone who joins is giving us the correct information about who they are. We also need to be sure that everyone has worked in a long-term care setting. It is important to our study results. The information that you provide in this survey will help us confirm your identity and that you are a long-term care worker. We will never contact your employer about your participation in the study.	N/A	N/A
Have you worked in a long-term care setting in the past 2 years? This includes nursing homes, skilled nursing facilities, assisted living facilities, home health care, hospice care, and retirement communities.	Yes	No
Below is a list of ways we can confirm you have worked in a long-term care setting in the past 2 years. Which of these can you do? Select all that apply. We will ask you to complete one of these options later in the survey.	Provide information from your workplace ID badge; Provide your Certification or Professional License Number; Email us from your work email account; Provide information from a recent pay stub (within the last 2 years);	None of the above
Are you pregnant or breastfeeding	No	Yes
Are you worried about the COVID-19 vaccines? If you have completed your initial COVID-19 vaccine series (1 Johnson & Johnson shot or 2 Pfizer/Moderna shots), have you had at least one booster shot since then?	Somewhat; Very OR No, I have not had any booster shots; I have not completed my initial series	Not at all; A little; AND Yes, I have had at least one booster shot; Not sure

4.3.2 Aim 3

Eligible participants for Intervention Consultations (as described in Table 1) will include LTCWs, including those who are members of our Stakeholder Advisory Group. We anticipate interviewing 10-12 participants for each round of consultations, until we reach thematic saturation.³²

For Implementation Consultations (as described in Table 1), our participants will be trial participants, study team members, and other key stakeholders identified through the “Adopters Implementers and Maintainers” brainstorm who may play roles in facilitating implementation in both the trial and sustainability phases. Reporting of Aim 3 activities will adhere to the Consolidate Criteria for Reporting Qualitative Research (COREQ) checklist³⁷.

4.3.3 Feasibility of Recruitment

We will utilize a diverse range of recruitment methods, both online and in-person. First, we plan to recruit and engage LTCWs using methods that have been previously effective for our partners at NACHA. We will therefore use NAHCA’s communication channels and their networks, consisting of social media followers and contacts with NAHCA registered employers. NAHCA membership is characterized by care workers who place value on professional development, however this does not apply to NAHCA non-members who are NAHCA followers on Facebook and YouTube. NAHCA has the capability to reach care workers in all 50 US states, and has members in all states, except Alaska. NAHCA has 24,500 members, with 22,685 subscribing to their list-serv, 2,150 YouTube subscribers, and 18,263 Facebook followers. Response rates to emails via their list-serv average a 33% open rate and a 12% click rate. Typical engagement on their Facebook posts ranges from 5% to 15%; and their YouTube videos reach 3,500 views on average. Using these estimates and given the survey-response incentives (\$30 per time-point), we anticipate interest from at least 2,722 LTCWs via the list-serv and 900 LTCWs via Facebook using a conservative 5% engagement level (3,622 in total). These numbers combined exceed the 1,800 LTCWs that we need to power the trial.

Our collaborator, [name], Clinical Director of the American Medical Director Association, has confirmed excellent collaborative arrangements with NAHCA to support recruitment. Both [name] (NAHCA CEO) and [name] (NAHCA COO) confirm that LTCWs can be effectively engaged using their membership list outreach methods and social media.

To further enhance diversity and reach, we will also utilize paid social media and online advertisements for study recruitment. Lastly, in-person recruitment strategies will include sharing recruitment materials via visits to LTC settings, conferences, and other events, and outreach to LTC settings with requests to display study recruitment materials.

[figure not shown]
We also intend to make all recruitment and other study materials available via mobile technology so that participants can easily access them on a telephone or tablet if they do not have reliable access to desktop computing.

4.4 Interventions and Comparator

4.4.1 Theory and Content Foundations

We designed two multi-component, interactive, online interventions (arms 1 and 2), informed by theoretical and practical information from the vaccine confidence and hesitancy literature. Notably, our intervention development and hypothesized mediators (see Figure 3) were initially informed by Peretti-Watel's vaccine hesitancy framework, which conceptualizes vaccine decision-making as a process. The framework also distinguishes between two types of vaccine hesitant people: 1) those with poor knowledge of and/or indifference to vaccination issues, and 2) those who are interested in vaccination issues and seek more information, yet are hesitant³⁸. We were also informed by the Report of the SAGE Working Group on Vaccine Hesitancy and its conceptualization of the “three Cs” of vaccine hesitancy: Confidence, Complacency and Convenience; and, we considered all three Cs³⁹. Additionally, our interventions were informed by the literature on reducing vaccine hesitancy, which suggests multi-component, dialogue-based interventions (such as conversation-based and social media interventions) are most effective, as well as those tailored for specific populations²². The interventions were co-designed, co-adapted, and pre-tested with LTCWs as well as NAHCA, IHI, and other co-investigators. The control arm (enhanced usual practice) is online COVID-19 vaccine information provided by the CDC.

Figure 3. Randomized controlled trial logic model

4.4.2 Development

The overall designs of the dialogue-based webinar and social media website interventions were informed by prior studies^{22,23,26} and developed using participatory research approaches^{40,41}. In developing content for each intervention, our goal was to maximize consistency of major topics across interventions, in order to isolate effects of each intervention delivery method.

To inform the intervention content, we initially derived topics from several sources, including social media monitoring, news surveillance, online public opinion polls^{42,43}, and peer-reviewed literature³⁹. The major topics for inclusion in both interventions were then refined via interviews with our LTCW partners as part of Aim 3. Additional information was gathered to inform the development of the social media website intervention, the details of which are published

elsewhere⁴⁴. The final list of major topics includes COVID-19 in general, vaccine benefits, vaccine risks, and vaccine development⁴⁴.

We also developed community standards to ensure all participants felt welcome and comfortable when engaging with the interventions. These standards, which are similar across both interventions, were based on the rules of existing vaccine discussion forums and were co-created with our LTCW partners⁴⁴. Also included in both interventions is a video that we developed featuring LTC residents voicing their views on why it is important for LTCWs to be vaccinated.

In response to low intervention exposure in one trial arm (webinar attendance) experienced in the first several weeks of data collection, we developed intervention ‘refreshers’ for each trial arm. The refreshers for trial arms 1 and 2 are briefer, modified versions of each primary intervention. They include content on new and emerging COVID-19 and vaccine-related topics, as well as popular questions trial participants have voiced through their primary intervention engagement. New and emerging topics were derived from several sources, including social media monitoring, news surveillance, online public opinion polls⁴⁵, and consultation with our LTCW partners and other stakeholders. Topics for inclusion were refined primarily via a poll to identify stakeholders’ information needs (process adapted from⁴⁶). Refreshers for trial arms 1 and 2 will be updated as required when there is sufficient new and emerging COVID-19 related public discourse.

